11.9. Immunogenicity

11.9.1. Cohorts and safety and immunogenicity sub-cohort

The primary analysis will be based on the ATP cohort for analysis of immunogenicity, which includes subjects from the safety and immunogenicity sub-cohort only. If, in any vaccine group, the percentage of vaccinated subjects with immunogenicity results excluded from the ATP cohort for analysis of immunogenicity is 5% or more, a second analysis based on the TVC, including subjects from the safety and immunogenicity sub-cohort only, will be performed to complement the ATP analysis.

11.9.2. Lab assays for immunogenicity

The following tables describe the lab assays that will be performed for immunogenicity assessment:

Table 8 Humoral Immunity (Antibody determination)

System	Component	Method	Kit/Manufacturer	Unit	Cut-off	Laboratory
Serum	Mycobacterium tuberculosis .M72 Ab.IgG	ELISA	Not Applicable	ELISA unit per millilitre	2.8	CEVAC or as designated by GSK Biologicals

Table 9 Cell-Mediated Immunity (CMI)

System	Component	Challenge	Method	Unit	Cut-off	Laboratory
Whole blood	CD4+/CD8+ T-cells expressing at least two immune markers (CD40L and/or IL-2 and/or TNF- α and/or IFN- γ) and any combination among CD40L, IFN- γ , IL-2 and TNF- α	M72	ICS - intracellular Cytokine Staining	Number of events per million cells	N/A	GSK or as designated by GSK

11.9.3. CMI and humoral immune responses

11.9.3.1. M72-specific CD4+/CD8+ T-cells expressing at least two different immune markers (IFN- γ and/or IL-2 and/or TNF- α and/or CD40L)

The following parameters will be tabulated at Days 0, 60 and Years 1, 2 and 3:

- Descriptive statistics of the frequency of M72-specific CD4+/CD8+ T-cells per million cells identified after *in vitro* stimulation expressing at least two different immune markers (IFN- γ and/or IL-2 and/or TNF- α and/or CD40L) after background subtraction for each treatment group.
- A box and whiskers plot of the frequency of M72-specific CD4+/CD8+ T-cells expressing at least two different immune markers (IFN- γ and/or IL-2 and/or TNF- α and/or CD40L) for the M72/AS01_E group.

- Comparison of the frequency of M72-specific CD4+/CD8+ T-cells expressing at least two different immune markers (IFN- γ and/or IL-2 and/or TNF- α and/or CD40L) between PRE and all time points for the M72/AS01_E group.
- Comparison of the frequency of M72-specific CD4+/CD8+ T-cells expressing at least two different immune markers (IFN- γ and/or IL-2 and/or TNF- α and/or CD40L) between PII(D60) and all time points for the M72/AS01_E groups.
- Percentage of responders for M72-specific CD4+/ CD8+ T-cells expressing at least two different immune markers (IFN- γ and/or IL-2 and/or TNF- α and/or CD40L) for treatment group, according to different responder definitions (see Section 12.2.2)

P-value below 5% will be used to identify events that are recognised as worthy of further investigation and such comparisons should be considered as purely exploratory. Such a caution is driven by the problem of unadjustment for multiplicity of tests, potentially a lack of power and that the clinical/biological relevance of the difference is not accounted for.

11.9.3.2. M72-specific CD4+/CD8+ T-cells expressing any combination of immune markers among IFN- γ , TNF- α , IL-2 and CD40L

The following parameters will be tabulated at Days 0, 60 and Years 1, 2 and 3:

- Descriptive statistics of the frequency of M72-specific CD4+/CD8+ T-cells per million cells identified after *in vitro* stimulation expressing any combination of immune markers among CD40L, IFN- γ , IL-2 and TNF- α , after background subtraction for each treatment group.
- A box and whiskers plot of the frequency of M72-specific CD4+/CD8+ T-cells expressing any combination of immune markers among CD40L, IFN- γ , IL-2 and TNF- α , for M72/AS01_E group.
- Descriptive statistics of the frequency of M72-specific CD4+/CD8+ T-cells expressing any combination of immune markers among IFN- γ , TNF- α and IL-2 for each treatment group.
- A box and whiskers plot of the frequency of M72-specific CD4+/CD8+ T-cells expressing any combination of immune markers among IFN- γ , TNF- α and IL-2 for the M72/AS01_E group.
- Descriptive statistics of the frequency of M72-specific CD4+/CD8+ T-cells expressing at least IL-2 for each treatment group (total IL-2).
- Descriptive statistics of the frequency of M72-specific CD4+/CD8+ T-cells expressing at least IFN- γ for each treatment group (total IFN- γ).
- Descriptive statistics of the frequency of M72-specific CD4+/CD8+ T-cells expressing at least TNF- γ for each treatment group (total TNF- α).
- Box and whiskers plots of the frequency of M72-specific CD4+/CD8+ T-cells expressing at least IL-2, at least IFN- γ or at least TNF- α for the M72/AS01_E group.

- Comparison of M72-specific CD4+ cells expressing at least IL-2, at least IFN- γ or at least TNF- α between PRE-and all timepoints for the M72/AS01_E group.
- Comparison of M72-specific CD4+ cells expressing at least IL-2, at least IFN- γ and at least TNF- α between PII(D60) and all timepoints for the M72/AS01_E group.

P-value below 5% will be used to identify events that are recognised as worthy of further investigation and such comparisons should be considered as purely exploratory. Such a caution is driven by the problem of adjustment for multiplicity of tests, potentially a lack of power and that the clinical relevance of the difference is not accounted for.

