11.9.3.3. Humoral immune responses

For anti-M72 antibody responses, the following parameters will be tabulated at Days 0, 60 and Years 1, 2 and 3:

- Geometric mean concentrations (GMCs) and seropositivity rates with 95% CIs for each treatment group.
- Evolution of GMCs and 95% CIs will be presented graphically for the M72/AS01_E group.
- Comparison of log (antibody concentrations) between PRE and all post-vaccination timepoints for the M72/AS01_E group
- GM of ratios of anti-M72 antibody titres at each post-vaccination timepoint over pre vaccination will be tabulated with 95% CI for each treatment group.

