13.3. Interpretation of analyses

For the analysis of the primary objective, a predefined success criterion and an appropriate type I error control are defined. The confirmatory secondary objective will be analysed only if the primary objective is met. Because of this hierarchy, the type I error is controlled. All other analyses will be descriptive with the aim to characterise the difference in TB incidence, reactogenicity and immunogenicity between groups. These descriptive analyses should not be interpreted.

The triggered primary analysis of efficacy is the analysis where all the alpha is spent.

The sensitivity analysis is for hypothesis generation and thus not confirmatory.

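### Every immunogenicity comparison in the SAP is within the M72/AS01E arm; no vaccine-versus-placebo estimate or test is planned, although the stated aim is the difference between groups

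*SAP*

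**What the plan says.** SAP 11.9.3.1 (CD4+/CD8+ cells with at least two markers) compares frequencies "between PRE and all time points for the M72/AS01_E group" and again "between PII(D60) and all time points for the M72/AS01_E groups". SAP 11.9.3.2 does the same for CD4+ cells expressing at least IL-2, IFN-γ or TNF-α: "between PRE-and all timepoints for the M72/AS01_E group", and Day 60 against the other time points. SAP 11.9.3.3 adds "Comparison of log (antibody concentrations) between PRE and all post-vaccination timepoints for the M72/AS01_E group".

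The two CMI sections attach a threshold: "P-value below 5% will be used to identify events that are recognised as worthy of further investigation", with the warning that "such comparisons should be considered as purely exploratory". The antibody section states no threshold. No test is named for any of these comparisons.

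Placebo is not left out of the tables. By treatment group, the SAP tabulates CMI descriptive statistics, responder percentages, antibody GMCs and seropositivity with 95% CIs, and geometric mean post/pre antibody ratios with 95% CIs. The box plots and the GMC evolution plot cover the vaccine arm only.

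SAP 13.3 says that the non-confirmatory analyses are descriptive, "with the aim to characterise the difference in TB incidence, reactogenicity and immunogenicity between groups", and that they are not to be interpreted. Protocol 11.10 states the same aim.

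**The concern.** A PRE-versus-post test in one arm has the null hypothesis of no change over time in vaccinees. That equals the null of no difference from placebo only if nothing but the vaccine moves the readout. The documents give reasons to doubt this over three years. Subjects are IGRA-positive at baseline and live in TB-endemic regions, and M72 is derived from two Mtb antigens, so natural boosting could shift both arms. Assay drift between sampling times could do the same.

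About 225 placebo subjects are sampled on the same schedule, so a randomised control exists but enters no contrast. What is at stake is the reading of the exploratory flags, mainly where the vaccine signal may be small or waning, and a stated between-group aim that no planned estimate meets.

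**Working it through.** **1. Count of planned comparisons, all in the M72/AS01E arm**
- Cells with at least two markers: 2 cell types × (4 PRE contrasts + 3 further Day 60 contrasts) = 14.
- Total IL-2, IFN-γ and TNF-α on CD4+ cells: 3 × (4 + 3) = 21.
- Antibody: 4, with no threshold stated.
- Between arms: 0.

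So 14 + 21 = 35 CMI contrasts fall under the 5% rule. Of these, 2 × 4 + 3 × 4 = 20 are PRE-versus-post and 15 are Day 60 versus later.

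**2. Inputs for the illustration**
- SD of the log10 value: 0.40, from the Amendment 4 entry in protocol Appendix C. Amendment 5 deleted that text. It referred to antibody and to CD4+ cells with at least two markers, so the SD for other readouts is unknown.
- Sub-cohort: about 225 per arm (protocol, Table 5); repeated with 180 per arm to allow for losses (assumed).
- Pre/post correlation ρ: not given, assumed 0.3 to 0.7.
- Shift shared by both arms: not given, assumed 0 to 0.10 log10.
- Test: not named in the SAP; a two-sided paired t-test at 5% is assumed.

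The current text has no immunogenicity precision figure to reproduce. The superseded half-widths do reproduce as t × 0.40/√n: 0.0525 at n = 225 (stated 0.052) and 0.0920 at n = 75 (stated 0.092).

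**3. Flag rate with no vaccine effect**

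SD of change = 0.40 × √(2(1 − ρ)), which is 0.473, 0.400 and 0.310 for ρ = 0.3, 0.5 and 0.7. Noncentrality = shift ÷ (SD of change/√n). For a 0.05 shift at n = 225 this is 1.58, 1.88 and 2.42. The noncentral t distribution gives, for n = 225:

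| Shared shift (log10) | Fold | ρ = 0.3 | ρ = 0.5 | ρ = 0.7 | Between-arm test of change |
|---|---|---|---|---|---|
| 0 | 1.00 | 5.0% | 5.0% | 5.0% | 5.0% |
| 0.02 | 1.05 | 9.7% | 11.6% | 16.1% | 5.0% |
| 0.05 | 1.12 | 35.1% | 46.3% | 67.4% | 5.0% |
| 0.10 | 1.26 | 88.4% | 96.2% | 99.8% | 5.0% |

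At 180 per arm, a 0.05 shift gives 29% to 58% and a 0.10 shift 81% to 99%.

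A separate simulation (1,500 trials, 200 per arm, ρ = 0.5, shift 0.05) gave 41.9% for the paired test and 5.5% for ANCOVA on arm and baseline.

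**4. Is a between-arm contrast feasible?**

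The detectable difference in change at 80% power is (1.960 + 0.842) × SD of change × √(2/n). At 225 per arm this is 0.125, 0.106 and 0.082 log10 (1.33-, 1.28- and 1.21-fold) for ρ = 0.3, 0.5 and 0.7. At 180 per arm it is 0.140, 0.118 and 0.092. Power for a two-fold difference (0.30 log10) is about 100% throughout.

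Baseline adjustment does no worse: its residual variance is (1 − ρ²)/(2(1 − ρ)) = (1 + ρ)/2 of the variance of change, or 0.65 to 0.85.

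**The case against.** The strongest defence is that these tests carry little weight by design. They are labelled exploratory, SAP 13.3 says the descriptive results are not to be interpreted, and no success criterion depends on them. The immunogenicity objective (SAP 3.2) names no comparator, and protocol 11.8.1.1 plans only within-group description. How far vaccinees' responses rise and persist is a valid one-arm question. By-group tables are a legitimate way to describe a difference, and a shared antibody shift would appear in the placebo post/pre ratio. The ATP immunogenicity cohort also removes subjects who develop TB or acquire HIV, two possible sources of change.

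Most of this stands, and it sets the severity. It does not supply the missing contrast. The SAP's caution cites multiplicity, power and relevance, but not the lack of a control. Two columns side by side also leave the reader to form the ratio and its uncertainty.

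A reader might go further and infer that any change shared with placebo will be declared a vaccine response. The documents do not support that:
- The SAP marks p below 5% only as deserving further study and never calls it a vaccine response.
- A small shared shift is flagged with some probability, not always (about 10% to 16% for 0.02 log10 under the assumptions above).
- The Day 60 contrasts concern persistence, so the argument about PRE does not describe them.
- The antibody comparison has no stated threshold.
- Placebo results are tabulated.

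**Conclusion.** The point holds in a limited form. No between-group immunogenicity estimate, interval or test is planned, and SAP 13.3 states a between-group aim. The 5% flag on the 20 CMI PRE-versus-post contrasts cannot distinguish a vaccine effect from a change common to both arms. That conclusion follows from the choice of contrast and needs no numerical assumption.

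The 35% to 67% figure does depend on assumptions: a superseded SD, an assumed correlation, an assumed paired t-test, and a 0.05 log10 drift that nothing in the documents establishes. With no drift, the within-arm test holds its 5%. The calculation also treats log10 values as normal. SAP 12.2.2 sets negative background-subtracted cell frequencies to 1 and antibody below the cut-off to half the cut-off, so values may pile up at a floor.

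Severity is low. A reader should not infer any effect on the primary or confirmatory secondary efficacy tests or on their type I error control, because neither uses these comparisons.

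**What to change.** In SAP 11.9.3.1 to 11.9.3.3, add for each readout an exploratory M72/placebo geometric mean ratio with 95% CI at Day 60 and Years 1, 2 and 3. Estimate it by regressing the log10 post-vaccination value on arm and the log10 Day 0 value, and name the method. Where many values sit at the assay floor, add a rank-based check. Apply the exploratory 5% flag to this contrast when judging response against placebo. Keep the within-arm PRE and Day 60 comparisons as descriptive summaries of rise and persistence; they need not be deleted. Record the addition in SAP section 14.

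The cost is SAP wording and one extra table per readout; all the data are already collected. Intervals will be somewhat wider than for a one-arm paired comparison. With equal variances, the ratio of standard errors is √(1 − ρ²) × √2 ÷ √(2(1 − ρ)) = √(1 + ρ), or about 1.14 to 1.30 for ρ from 0.3 to 0.7.

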11.9.3.3. Humoral immune responses

For anti-M72 antibody responses, the following parameters will be tabulated at Days 0, 60 and Years 1, 2 and 3:

- Geometric mean concentrations (GMCs) and seropositivity rates with 95% CIs for each treatment group.
- Evolution of GMCs and 95% CIs will be presented graphically for the M72/AS01_E group.
- Comparison of log (antibody concentrations) between PRE and all post-vaccination timepoints for the M72/AS01_E group
- GM of ratios of anti-M72 antibody titres at each post-vaccination timepoint over pre vaccination will be tabulated with 95% CI for each treatment group.

11.10. Reactogenicity

11.10.1. Cohorts

The primary analysis will be based on the TVC. If, in any vaccine group, the percentage of vaccinated subjects excluded from the ATP cohort for analysis of safety is more than 5%, a second analysis based on this ATP cohort for analysis of safety will be performed to complement the TVC analysis.

Analyses of solicited (local and general) AEs and clinical laboratory observations will be performed for the safety and immunogenicity sub-cohort only.

11.10.2. Exposure

An overview of the number of vaccine doses received will be displayed by treatment group

11.10.3. Compliance

The compliance in returning symptoms sheets (SS) will be described in the safety and immunogenicity sub-cohort.

The number of doses administered, the number of doses not given according-to-protocol, the number of SS transcribed for local and general symptoms, and the compliance for local and general symptoms will be tabulated by treatment group. Compliance (%) is defined as the number of (local/general) SS completed divided by the number of doses administered for a specified group. The number of doses not given according-to-protocol is the number of doses administered at wrong site, or administered using a wrong route as compared to the protocol specifications (per protocol, site is deltoid and route is intramuscular)

11.10.4. All symptoms

This analysis will be performed in the safety and immunogenicity sub-cohort.

- The percentage of subjects with at least one local AE (solicited and/or unsolicited), with at least one general AE (solicited and/or unsolicited) and with any AE during the solicited follow-up period (Day 0 to Day 6) will be tabulated by treatment group with exact 95% CI after each vaccine injection and overall.
- The percentage of doses followed by at least one local AE (solicited and/or unsolicited), by at least one general AE (solicited and/or unsolicited) and by any AE will be tabulated by treatment group, overall vaccination course, with exact 95% CI.

The same tabulations will be done for grade 3 AEs and for AEs causally related to vaccination.

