3. STUDY DESIGN OVERVIEW

Figure 2 Overview of the study design (Amended: 29 January 2014)

Protocol waivers or exemptions are not allowed with the exception of immediate safety concerns. Therefore, adherence to the study design requirements, including those specified in the outline of study procedures (Section 6.5), are essential and required for study conduct.

- **Experimental design:** Phase IIb, randomised, double-blind, controlled, multi-centre, efficacy study with two parallel groups.
- **Duration of the study:** the duration of the study will be approximately 37 months for each subject from screening up to end of efficacy follow-up.
 - Epoch 001: Primary starting visit 1 (screening visit) and ending visit 10 (Month 36).
- **Study groups:** Study groups and treatments foreseen in the study are presented in [Table 1](#) and [Table 2](#).

Table 1 Study groups and epochs foreseen in the study (Amended: 29 January 2014)

Study Groups	Number of subjects	Age (Min - Max) (age unit)	Epoch 001
M72AS01	1753	18 years - 50 years	x
Control	1753	18 years - 50 years	x

Table 2 Study groups and treatment foreseen in the study

Treatment name	Vaccine/Product name	Study Groups	
		M72AS01	Control
M72/AS01 _E	M72	x	
	AS01 _E	x	
Placebo	Placebo pellet		x
	Placebo adjuvant		x

- **Control:** placebo control.
- **Vaccination schedule:** Subjects will receive 2 doses of M72/AS01_E or placebo, according to their random assignment, one month apart (Day 0 and Day 30) by intramuscular injection in the deltoid region of the arm.
- **Treatment allocation:** Randomised 1:1. Randomisation will occur at the day of first vaccination (Day 0). Refer to Section 6.2 for a detailed description of the randomisation method.
- **Blinding:** Double-blind (Table 3). Refer to Section 6.3 for method of blinding.

Table 3 Blinding of study epochs

Study Epochs	Blinding
Epoch 001	double-blind

- **Sampling schedule (Amended: 29 January 2014):**
 - Blood samples will be collected in the safety and immune sub-cohort for evaluation of biochemistry/haematology parameters (Days 0, 7, 30 and 37), CMI responses (Days 0, 60 and Years 1, 2 and 3) and humoral immune responses (Days 0, 60 and Years 1, 2 and 3). **Vitamin D levels will be measured at Day 0.**
 - Blood samples will be collected for QFTG testing at **screening** for all subjects.
 - **A respiratory sputum sample will be collected prior to vaccination in all subjects for nucleic acid amplification test to rule out pulmonary TB.**

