6.2.3. Allocation of subjects to assay subsets

Approximately **450** subjects will be included in the safety and immune sub-cohort. These subjects will be enrolled at selected centres. Blood sampling and safety assessment will be performed as described in [Table 4. Distribution of subjects in the sub-cohort is presented in Table 5.](#) (Amended: 29 January 2014)

Table 5 Distribution of subjects in the sub-cohort

Sub-cohort	Treatment group	N to be enrolled
Safety and immune sub-cohort	M72AS01	Approximately 225
	Control	Approximately 225

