11.9. Analysis of safety

The primary analysis will be based on the TVC for analysis of safety. If, in any vaccine group, the percentage of vaccinated subjects excluded from the ATP cohort for analysis of safety is 5% or more, a second analysis based on the ATP cohort for analysis of safety will be performed to complement the TVC analysis.

Analyses of solicited (local and general) AEs and clinical laboratory observations will be performed for the safety and immune sub-cohort only. (Amended: 29 January 2014)

The following analyses will be performed:

- The percentage of subjects with at least one local AE (solicited and/or unsolicited), with at least one general AE (solicited and/or unsolicited) and with any AE during the solicited follow-up period will be tabulated with exact 95% CI after each vaccine dose and overall. The percentage of doses followed by at least one local AE (solicited and/or unsolicited), by at least one general AE (solicited and/or unsolicited) and by any AE will be tabulated, overall vaccination course, with exact 95% CI.
- The percentage of subjects reporting each individual solicited local and general AE during the solicited follow-up period will be tabulated with exact 95% CI. The percentage of doses, followed by each individual solicited local and general AE will be tabulated, overall vaccination course, with exact 95% CI.
- Injection site swelling and redness will be analysed using a 3-grade evaluation system [0 mm **to 20 mm** (grade 0); **≥20 to 50 mm** (grade 1); **> 50 to 100 mm** (grade 2); **> 100 mm** (grade 3)]. **(Amended: 29 January 2014)**
- Occurrence of fever will be reported per 0.5°C cumulative increments. Duration and prevalence of fever will be presented. Fever will also be analysed using a 3-grade evaluation system [**< 37.5°C** (grade 0); **≥ 37.5°C but ≤ 38.0°C** (grade 1); **> 38.0°C but ≤ 39.5°C** (grade 2); **> 39.5°C** (grade 3)].
- The same tabulation will be performed for grade 3 AEs and for AEs with relationship to vaccination.
- The percentage of subjects with at least one report of unsolicited AE classified by the Medical Dictionary for Regulatory Activities (MedDRA) and reported up to 30 days after vaccination will be tabulated with exact 95% CI. The same tabulation will be performed for grade 3 unsolicited AEs and for unsolicited AEs with a relationship to vaccination.
- The percentage of subjects reporting AEs resulting in a medically attended visit will also be tabulated.

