11.11. Solicited symptoms

The analysis of solicited symptoms will be performed in the safety and immunogenicity sub-cohort.

The number and percentage of subjects reporting each individual solicited local (any, grade ≥ 2 , grade 3) and general (any, related to vaccination, grade ≥ 2 , grade 3, grade ≥ 2 related to vaccination and grade 3 related to vaccination) AE during the solicited follow-up period will be tabulated by treatment group with exact 95% CI.

The number and percentage of doses followed by each individual solicited local (any, grade ≥ 2 and grade 3) and general (any, related to vaccination, grade ≥ 2 , grade 3, grade ≥ 2 related to vaccination and grade 3 related to vaccination) AE will be tabulated by treatment group, overall vaccination course, with exact 95% CI.

The percentage of doses followed by each individual solicited local and general (any, grade 3) AE will be presented in a bar chart by treatment group, overall vaccination course (2 doses combined), with exact 95% CI.

Occurrence of fever will also be reported per 0.5°C cumulative increments.

The number of days with a solicited symptom during the solicited follow-up period will also be presented by treatment group. The same tabulations will be done for grade 3 AEs and for general AEs with relationship to vaccination.

The number of days with a solicited symptom during the solicited follow-up period and beyond will also be presented by treatment group. The same tabulations will be done for grade 3 AEs and for general AEs with relationship to vaccination.

The number of solicited local and general symptoms ongoing beyond the 7-day post-vaccination period is given by treatment group as well as descriptive statistics (Q1, median, Q3) concerning the time-to-resolution (in days from the last day of the follow-up period to the last day the symptom was observed).

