11.13. Unsolicited symptoms

The proportion of subjects/doses with at least one report of unsolicited AE classified by the Medical Dictionary for Regulatory Activities (MedDRA) reported during the 30-day follow-up period (Days 0 to 29) will be tabulated with exact 95% CI by treatment group.

The same tabulations will be done for grade 3 AEs, AEs related to vaccination, grade 3 events related to vaccination and AEs resulting in a medically attended visit.

As only the subjects part of the safety and immunogenicity sub-cohort have a diary card to collect the solicited AEs, those symptoms (redness, swelling, pain at injection site, fever, headache, respiratory symptoms, malaise, myalgia)) reported for the other subjects were recorded in the Case Report Form (CRF) section on unsolicited symptoms.

Therefore to assess the impact of this situation, the following analyses will be proposed:

- The same analysis will be produced for the subjects with diary cards (part of the safety and immunogenicity sub-cohort).
- The proportion of subjects/doses with at least one report of unsolicited AE classified by MedDRA reported during the 7-day follow-up period (Days 0 to 7) will be tabulated with exact 95% CI by treatment group. Idem for grade 3 AEs, AEs related to vaccination, grade 3 events related to vaccination.
- The proportion of subjects/doses with at least one report of unsolicited AE classified by MedDRA reported after the 7-day follow-up period (Days 7 to 29) will be tabulated with exact 95% CI by treatment group. Idem for grade 3 AEs, AEs related to vaccination, grade 3 events related to vaccination.

The proportion of subjects with at least one report of unsolicited AE associated to the respiratory system classified by the MedDRA reported during the 90-day post-vaccination follow-up period (on or after Day 0 to Day 89) will be tabulated with exact 95% CI by treatment group, for all subjects in the TVC population.

The same tabulation will be done for, grade 2 or 3 AE associated to the respiratory system, grade 3 AE associated to the respiratory system, AE associated to the respiratory system related to vaccination, grade 2 or 3 AE associated to the respiratory system related to vaccination and grade 3 AE associated to the respiratory system related to vaccination.

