12.2.3. Methodology for computing CIs

All CIs computed will be two-sided 95% CIs.

- The exact 95% CIs for a proportion within a group will be the Clopper-Pearson exact CI. [\[Clopper. 1934\]](#).
- The 95% CI for GMCs will be obtained within each group separately. The 95% CI for the mean of log-transformed concentration will be first obtained assuming that log-transformed values were normally distributed with unknown variance. The 95% CI for the GMCs will then be obtained by exponential transformation of the 95% CI for the mean of the log-transformed concentration.

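### Exact confidence intervals on per-dose AE percentages ignore that each subject contributes up to two doses; if the two reactions are positively correlated, the intervals for all but rare events are too narrow.

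*SAP*

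**What the plan says.** The design gives each participant two injections: "Subjects will receive 2 doses of M72/AS01_E or placebo, according to their random assignment, one month apart" (protocol section 3). Solicited AEs are analysed in the safety and immunogenicity sub-cohort, with "Approximately 225" subjects per group (protocol 6.2.3).

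Per-dose percentages with exact intervals appear in these places:

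- SAP 11.10.4, for any local, any general and any AE: "by any AE will be tabulated by treatment group, overall vaccination course, with exact 95% CI". The same is repeated for grade 3 and for related AEs.
- SAP 11.11, for each solicited AE, in tables and in a figure that "will be presented in a bar chart by treatment group, overall vaccination course (2 doses combined), with exact 95% CI".
- SAP 11.13, for MedDRA-coded unsolicited AEs: "The proportion of subjects/doses with at least one report of unsolicited AE", again with exact 95% intervals.
- Protocol 11.9, for all AEs and for each solicited AE, starting with "The percentage of doses followed by at least one local AE (solicited and/or unsolicited". For unsolicited AEs, protocol 11.9 asks only for percentages of subjects; the per-dose version comes from the SAP.

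The method is defined once, in SAP 12.2.3: "The exact 95% CIs for a proportion within a group will be the Clopper-Pearson exact CI". That sentence sits under immunogenicity. SAP 12.3, on safety calculations, names no other interval method and makes no allowance for two doses in one person.

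Per-subject percentages with exact intervals are also planned: after each injection and overall in 11.10.4, and for each solicited AE in 11.11.

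**The concern.** Clopper-Pearson inverts a binomial distribution, which requires independent trials. Two injections of the same product in the same person a month apart are unlikely to meet that: someone who reacts to the first is plausibly more likely to react to the second. Under positive correlation, 450 doses from 225 people carry less information than 450 independent doses, and the interval is narrower than its label claims.

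What is at stake is the stated precision of the per-dose reactogenicity display. Because these analyses are descriptive, the interval is the only statement of uncertainty beside the percentage. The one solicited-AE figure described in the SAP text is drawn per dose.

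**Working it through.** **Inputs.** Two doses per subject (protocol section 3). N = 225 subjects per group (protocol 6.2.3), so 2 x 225 = 450 doses. Clopper-Pearson at two-sided 95% (SAP 12.2.3). The documents give neither a per-dose AE rate p nor a within-subject correlation rho. I assume p from 0.5% to 40% and rho from 0 to 0.6, with rho = 1 as the limit. Every subject is taken to receive both doses. The plan states no interval width, so there is no figure of its own to reproduce.

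**Step 1, variance.** For two equally likely, correlated outcomes per subject,

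Var(p-hat) = p(1-p)(1+rho) / (2N),

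against p(1-p)/(2N) under independence. The design effect is 1+rho, and the effective number of doses is 450/(1+rho): 375, 321 and 281 at rho = 0.2, 0.4 and 0.6, and 225 at rho = 1.

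**Step 2, width.** At p = 40% (180 of 450 doses), the Clopper-Pearson half-width is 4.62 points. Multiplying by sqrt(1+rho):

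- rho = 0.2: 4.62 x 1.095 = 5.06
- rho = 0.4: 4.62 x 1.183 = 5.47
- rho = 0.6: 4.62 x 1.265 = 5.84
- limit, rho = 1: factor sqrt(2) = 1.41

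**Step 3, coverage.** Let p11 = p^2 + rho p(1-p). A subject contributes 2, 1 or 0 events with probabilities p11, 2(p - p11) and 1 - 2p + p11. For p = 0.4 and rho = 0.4: p11 = 0.16 + 0.4 x 0.24 = 0.256, giving 0.256, 0.288 and 0.456. Convolving over 225 subjects gives the exact distribution of the total. Coverage is the probability of totals whose Clopper-Pearson interval on 450 contains p.

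| Rate | rho 0 | 0.1 | 0.2 | 0.4 | 0.6 |
|---|---|---|---|---|---|
| 40% | 95.2% | 94.0% | 92.8% | 90.5% | 88.1% |
| 10% | 95.9% | 94.9% | 93.8% | 91.6% | 89.4% |
| 2% | 95.9% | 94.8% | 93.8% | 91.5% | 89.2% |
| 1% | 97.3% | 96.5% | 95.6% | 93.7% | 91.3% |
| 0.5% | 99.2% | 98.8% | 98.5% | 97.8% | 97.2% |

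Hand check with the normal approximation, 2 Phi(1.96/sqrt(1+rho)) - 1: at rho = 0.4, 1.96/1.183 = 1.657, which gives 90.2%.

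Unequal rates at the two doses change little. With 40% then 60%, coverage is 93.1% at rho = 0.3 and 90.9% at rho = 0.5.

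**Step 4, the all-subjects table.** The main unsolicited-AE table is not restricted to the sub-cohort. With 1753 subjects per group (3506 doses) and p = 40%, coverage is 92.7%, 90.3% and 88.0% at rho = 0.2, 0.4 and 0.6, so the larger group does not help. Widths scale by sqrt(450/3506) = 0.358, so the half-width is about 4.62 x 0.358 = 1.65 points. At rho = 0.4 the missing width is about 1.65 x 0.183 = 0.3 points, against 5.47 - 4.62 = 0.85 points in the sub-cohort.

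**The case against.** The case for leaving the plan alone has four parts.

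*Valid intervals are already there.* The per-subject intervals in 11.10.4 and 11.11 count each person once. SAP 11.12 summarises large swelling per subject. This stands, and it confines the problem to the per-dose columns and the bar chart.

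*Nothing turns on these intervals.* SAP 13.3 classes the safety analyses as descriptive, no success criterion uses them, and the holding rules in protocol 6.4.5.4 count subjects. A reader might infer that the trial's main reactogenicity conclusions rest on faulty intervals. The documents do not support that: they give the per-dose display no such status, and only the bar chart has no per-subject counterpart in the SAP text.

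*The size is assumed.* This also stands. A reader might infer that the intervals miss 95% coverage whatever the data. They do not. Clopper-Pearson is conservative, so at rho = 0.1 coverage is about 94% to 95% for rates of 2% to 40%, and for 0.5% events in the sub-cohort it stays above 97% up to rho = 0.6.

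*The usual remedy can be worse for rare events.* In simulations with 225 subjects, a 0.5% rate and rho of 0.1 to 0.4, a robust Wald interval covered 83% to 88%. A logit-link GEE interval was undefined, with zero events, in 12% to 17% of arms. Grade 3 rows may well be this sparse. This does not rescue the planned interval at common rates, but it does restrict the choice of fix.

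A reader might also infer a separate bias, because some dose 1 reactions bar dose 2 and so the number of doses depends on the outcome. The stated quantity is the percentage of administered doses, so weighting by doses given is what it means. A clustered interval leaves that weighting unchanged, the calculations here give everyone two doses, and I do not count it as an error.

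**Conclusion.** The point holds, conditionally and at modest size. As written, the plan puts an independent-trials interval on paired observations. If reactions to the two doses are positively correlated, which is the natural expectation but not a figure in the documents, the per-dose intervals are too narrow for events at rates of about 2% or more in the sub-cohort. Coverage at a 40% rate is about 93%, 90% and 88% for rho = 0.2, 0.4 and 0.6. The width error cannot exceed a factor of 1.41, because there are at most two doses per subject. At a 1% rate, coverage falls below 95% only from about rho = 0.3.

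The same proportional loss applies to the all-subjects unsolicited table, with smaller absolute widths. Efficacy, the per-subject safety intervals and the holding rules are unaffected. Applying Clopper-Pearson to safety is an inference from its being the only exact method defined. It is a reasonable one, and SAP 12.3 offers nothing else.

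**What to change.** 1. Leave the exact per-subject intervals in SAP 11.10.4, 11.11 and 11.13 as they are.
2. For per-dose percentages, choose one of two options and state it in SAP 12.3:
   - show the percentage without an interval; or
   - use a subject-clustered interval that also works at low counts. One example is Clopper-Pearson on the effective sample size, i.e. doses divided by the design effect estimated from the between-subject variance (floored at 1), with plain Clopper-Pearson where there are no events. I simulated this with 225 subjects, rates of 0.5% to 40% and rho of 0 to 0.6 (20,000 arms per setting); coverage was 94.7% or higher throughout.
3. Base the bar chart in SAP 11.11 on per-subject rates or on the clustered interval.
4. Say in SAP 12.3 which exact method applies to safety proportions, and list the departure from protocol 11.9 in SAP section 14.

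The cost is a few lines of SAP text and, for the second option, a short routine with a zero-event branch. Per-dose intervals become wider by about sqrt(1+rho). No new data are needed and the design does not change.
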